#### **7.1.1. GI Intolerance Management**

For participants experiencing GI intolerance, all reasonable, medically appropriate efforts should be made to support them in adhering to scheduled dose/dose escalations. Depending on the specific GI AEs and per the investigator's judgement, this may include the use of stool softeners, laxatives, enemas, and/or the anti-emetic ondansetron.

#### **7.2. Number of Participants**

One hundred fifty (150) participants will be enrolled; 50 participants per treatment arm.

#### **7.3. Treatment Assignment**

##### **7.3.1. Assignment of Screening and Randomization Numbers**

All consented participants will be given a unique screening number that will be used to identify the subject for all procedures that occur before randomization or allocation. Each subject will be assigned only one screening number. Screening numbers must not be reused for different participants.

Participants will be assigned to either placebo, K-757 alone, K-757+K-833. Participants who meet all criteria for enrollment will be randomized at Visit 2 and assigned to their respective treatment groups via IWRS using the following stratification variables: gender (male/female). There will be equal randomization to the treatment arms (1:1:1). The randomization scheme will be performed using IWRS that will ensure balance between treatment arms.

### **7.3.2. Study Drug Assignment**

The randomization number encodes the subject assignment to either K-757 alone, K-757 + K-833, or placebo, according to the randomization schedule generated before the study. Each subject will be dispensed study drug in a double-blinded manner, labeled with his/her unique randomization number, throughout the study.

### **7.3.3. Subject Replacement**

No participants will be replaced.

### **7.4. Dose Adjustment Criteria**

No dose adjustment will be allowed, as this is a forced titration study.

### **7.5. Criteria for Study Termination**

The overall study begins when the first subject signs the study informed consent form.

The overall study ends when the last subject completes the last planned or follow-up visit/interaction associated with a planned visit (this can be a phone contact), discontinues from the study, or is lost to follow-up (e.g., the Investigator is unable to contact the subject).

Study discontinuation because of non-safety reasons, such as the following:

- A finding (e.g., PK, PD, efficacy) from another nonclinical or clinical study using the study treatment(s) results in the study being stopped for a non-safety related reason.
- The study is stopped because of nonscientific and non-safety reasons, such as slow enrollment.

Study discontinuation because of safety reasons:

Early study termination because of unanticipated concerns of safety to the study participants arising from clinical or nonclinical studies with the study treatment(s), comparator(s), drug(s) of the same class, or methodology(ies) used in this study.

#### **7.5.1. Criteria for Premature Termination or Suspension of Trial or Site**

A study site may be terminated prematurely or suspended if the site (including the Investigator) is found in significant violation of Good Clinical Practice (GCP), protocol, or contractual agreement, or is unable to ensure adequate performance of the study, or as otherwise permitted by the contractual agreement.

**7.5.2. Procedures for Premature Termination or Suspension of the Trial or Site**

In the event that the Sponsor, an Investigational Review Board (IRB)/Independent Ethics Committee (IEC), or regulatory authority elects to terminate or suspend the study or the participation of an investigational site, a study-specific procedure for early termination or suspension will be provided by the Sponsor; the procedure will be followed by applicable investigational sites during the course of termination or study suspension.

## 8. SELECTION AND WITHDRAWAL OF PARTICIPANTS

### 8.1. Subject Inclusion Criteria

All entry criteria, including laboratory test results, need to be confirmed before administration of the first dose of study drug.

In order to be eligible for participation in this trial, the subject must:

1. Understand the trial procedures and agree to participate by providing written informed consent prior to trial related activities. Trial-related activities are any procedures that are carried out as part of the trial, including activities to determine suitability for the trial.
2. Be willing and able to comply with all trial procedures and restrictions, including following study diet requirements.
3. Be a male or female, age 18 to 70 years of age, inclusive, at the time of signing informed consent.
4. Have a body mass index (BMI) of 30.0 to 40.0. kg/m^2, inclusive at screening.
5. History of at least one self-reported unsuccessful dietary effort to lose body weight.
6. Be weight stable (<5% variation) over the last 3 months (by subject report).
7. Be a nonsmoker or has smoked  $\leq 10$  cigarettes per week for at least 3 months and agrees not to exceed this for the duration of study participation; has not used other nicotine containing products (e.g. other forms of tobacco, nicotine patch, e-cigarettes, vapes) for at least 3 months and agrees to abstain from such products throughout study participation.
8. Meet the following birth control requirements:
  - a. Is a male subject who agrees to **all** of the following:
    - If partner is a non-pregnant female of child-bearing potential: To use an appropriate method of contraception, which must include a condom with spermicidal cream or jelly, from the first dose of study drug until 14 days after the last dose of study drug. A male subject who has had a vasectomy procedure must use a condom, but is not required to use spermicidal cream or jelly.
    - If partner is pregnant, to use a condom
    - Note: Contraception/condom requirements are waived if partner is NOT of child-bearing potential (i.e. is male or is a female who is post-menopausal or surgically sterile [post-hysterectomy, post-bilateral oophorectomy, and/or post-bilateral salpingectomy]).
    - To not donate sperm from the first dose of study drug until 14 days after the last dose of study drug.

OR

- b. Is a female who is of non-childbearing potential defined by at least 1 of the following criteria:

- Postmenopausal (aged >45 years and with a minimum of 12 months of spontaneous amenorrhea with a Screening serum follicle-stimulating hormone (FSH) level in the menopausal range established for the central laboratory.
- Post hysterectomy, bilateral oophorectomy or bilateral salpingectomy, based on the subject's recall of their medical history.

OR

- c. Is a female of reproductive potential and:
- agrees to not donate eggs from the first dose of study drug until 14 days after the last dose of study drug.
  - agrees to remain abstinent from heterosexual activitya or
  - agrees to use (or have their partner use) a birth control method that is highly effective and has low user dependency from the first dose of study drug until 14 days after the last dose of study drug. Acceptable methods of birth control are:
    - Progestogen-only implant (e.g. etonogestrel implant)
    - Intrauterine device (IUD)
    - Intrauterine hormone-releasing system (IUS)
    - Bilateral tubal occlusion
    - Vasectomized partner

a Abstinence can be used as the sole method of contraception if it is in line with the subject's preferred and usual lifestyle and if considered acceptable by local regulatory agencies and ethics committees. Periodic abstinence (e.g., calendar, ovulation, sympto-thermal, post-ovulation methods, etc.) and withdrawal are not acceptable methods of contraception.

This condition is waived if the subject is proven to have no child-bearing potential (eg, hysterectomy).

## 8.2. Subject Exclusion Criteria

Participants are excluded from the trial if any of the following criteria apply:

### Glycemia related:

1. Has a HbA1c  $\geq 6.5\%$  (48 mmol/mol) as measured by the central laboratory at screening.
2. Has a history of clinically significant endocrine disease including T2DM.

**Note:** A history of hypothyroidism does not require exclusion if the subject has been on a stable dose of thyroid hormone replacement (thyroxine) for at least 3 months prior to screening and the screening TSH is within the central laboratory normal range.

3. Has a history of type 1 or type 2 diabetes mellitus.
4. Had treatment with any glucose-lowering agent(s) within 90 days before screening.

### Obesity related:

5. Had treatment with any medication approved for the treatment of obesity or any investigational agent being tested for obesity treatment within the past 6 months before screening. This includes agents that are approved as a component of a multi-drug combination treatment for obesity, regardless of the purpose of current use, with the exception of bupropion.

Bupropion, which is a component of the naltrexone-bupropion combination approved for weight loss (Contrave™), is also approved as a single agent for the treatment of depression. Bupropion is not exclusionary if it is being used for treatment of depression and eligibility criteria for anti-depressant medication stability prior to screening are met (see Exclusion Criterion #12).

6. Has been treated with/used any other medication, supplement, or device for the purpose of promoting weight loss (regardless of whether they are approved or promoted for the purpose of weight loss) in the 90 days prior to screening.
7. Treatment with any GLP-1 receptor agonist in the prior 6 months.
8. Participation in an organized weight reduction program (e.g. Weight Watchers) within 90 days of screening.
9. Had a previous or has a planned (during the trial period) obesity treatment with surgery or a weight loss device. **Note:** Prior liposuction and/or abdominoplasty are not exclusionary if performed >2 years before screening).
10. Has uncontrolled thyroid disease, defined as thyroid stimulating hormone (TSH) outside (above or below) the reference range of the central laboratory at screening or has any history of Grave's disease unless all 3 of the following criteria are all met: 1. Grave's disease was treated with total thyroidectomy >2 years prior to screening, 2. There has been no recurrence of hyperthyroidism since thyroidectomy, **and** 3. TSH is the reference range of the central laboratory at screening.
11. Obesity is induced by an endocrine disorder (e.g. Cushing's disease).

#### Mental health:

12. Has a history of major depressive disorder within 2 years before screening, unless **all** of the following criteria are met:
  - a. the depressive disorder has always been unipolar (no history of mania or hypomania)
  - b. in the opinion of the investigator, depressive symptoms have been stable and well controlled for  $\geq 2$  years prior to screening
  - c. any anti-depressant drug-treatment regimens (medications and doses) have been stable for  $\geq 6$  months prior to screening
13. Has any history of other severe psychiatric disorder (e.g., schizophrenia, bipolar disorder) that was not clearly attributable to an intercurrent event/life circumstance, self-limited and fully resolved  $\geq 1$  year prior to screening.
14. On the screening Patient Health Questionnaire-9 (PHQ-9), has an overall score  $\geq 15$  **or** has a score  $>0$  for Question # 9 (Thoughts that you would be better off dead or of hurting yourself). **Note:** See Section 15.1.6 regarding requirements for referral to a mental health professional based on the results of the screening PHQ-9 assessment ([Appendix C](#)).

15. Has any lifetime history of suicide attempt or suicidal behavior. **Note:** Suicidal behavior includes any acts/preparation toward making a suicide attempt whether the attempt is never initiated or is initiated but interrupted by self or another person.
16. Use of any anti-psychotic agents for any purpose within 2 years before screening.
17. Use of the following prohibited agents:
  - Prohibited classes of anti-depressant agents (see Section 10.1) for any purpose, within 6 months of screening. **Note:** Use of allowable classes of anti-depressant agents (see Section 10.1) is permitted **only** if the anti-depressant regimen (agents **and** doses) has been stable for  $\geq 6$  months prior to screening and is not anticipated to change during the trial period.
  - Stimulant medications including amphetamines (e.g. dextroamphetamine, lisdexamfetamine) and methylphenidate/dexmethylphenidate within 6 months of screening.

General Safety:

18. Has a recent history (within the past 3 years of screening visit) or current diagnosis or evidence of hematological, immunological, renal, respiratory, neurologic, or genitourinary abnormalities or diseases that, per the investigator's judgement, may jeopardize the subject's safety or compliance with the protocol, or otherwise interfere with interpretation of efficacy and/or safety results.
19. Has a recent history (within past 3 years of screening visit) or current diagnosis of any of the following GI (gastrointestinal) related diseases: intestinal obstruction, GI perforation, adhesions, *Clostridium difficile* colitis or have had recent unexplained GI bleeding within 3 months prior to screening.
20. Has any history of pancreatitis (acute or chronic), gastroparesis, ischemic colitis, inflammatory bowel disease (IBD), or celiac disease.
21. Has a personal or first-degree relative history of multiple endocrine neoplasia type 2 or medullary thyroid carcinoma.
22. Has a screening estimated Glomerular Filtration Rate (eGFR) estimated with the Modification of Diet in Renal Disease (MDRD) equation of  $< 60$  ml/min/1.73 m^2.
23. Has a history of malignant neoplasms within the past 5 years prior to screening. Basal and squamous cell skin cancer and any carcinoma in-situ are allowed if they have received treatment and follow-up consistent with local standard of care.
24. Has any history of cardiovascular disease including stable and unstable angina pectoris, myocardial infarction, transient ischemic attack, stroke, cardiac decompensation, clinically significant arrhythmias, clinically significant conduction disorders, or any history or heart failure.
25. Has surgery scheduled for the duration of the trial, except for minor surgical procedures, in the opinion of the investigator.
26. Has a history of human immunodeficiency virus (HIV) infection.

27. Has any active liver disease other than non-alcoholic fatty liver disease (NAFLD), or any gallbladder disease that has been active/symptomatic within 6 months of screening.
28. Has a positive test result for hepatitis B surface antigen (Ag), hepatitis C virus antibody, HIV antibody, at the Screening Visit. Note: Participants with positive hepatitis B virus or hepatitis C virus serology may be enrolled if quantitative polymerase chain reaction for hepatitis B virus or hepatitis C virus ribonucleic acid is negative.
29. Has alanine aminotransferase or aspartate aminotransferase (ALT or AST) of  $>2.0X$  upper limit of normal (ULN) or total bilirubin  $>1.5X$  ULN at the Screening visit. Note: An isolated bilirubin  $>1.5X$  ULN is acceptable if bilirubin is fractionated, and direct bilirubin is within the laboratory normal range).
30. Has serum amylase or lipase  $>1.2X$  the ULN at the Screening Visit.
31. Has a triglyceride value  $>600\text{mg/dL}$  at the Screening visit (if value is  $\geq 600\text{ mg/dL}$  and the sample was obtained in the non-fasted state, a repeat fasting determination may be obtained to assess eligibility).
32. Has a corrected QT interval to Fridericia's formula (QTcF)  $>450$  milliseconds (msec) for males and  $>470$  msec for females at screening.
33. Has a mean value for triplicate seated systolic blood pressure  $>160$  mmHg and/or diastolic blood pressure (BP)  $>95$  mmHg measured after at least 5 minutes at rest at the Screening Visit. **Note:** If a subject's BP is exclusionary on the first triplicate assessment at the Screening visit, they may have 1 repeat triplicate BP assessment at that visit after another rest of at least 10 minutes. If a participant's BP is exclusionary on 2 assessments at the Screening visit, the investigator can, at their discretion, adjust and/or add anti-hypertensive medications and re-assess triplicate BP up to twice at the Randomization visit (Visit 2). Anti-hypertensive regimens must align with the requirements detailed in Section 10.1 ( $\leq 2$  agents that do **not** include verapamil). If a participant's BP is exclusionary at the Screening visit and the randomization visit (Visit 2), they must be excluded.
34. Has known history or suspected abuse of alcohol or recreational drugs.
35. Has excessive consumption of alcohol within 6 months prior to screening ( $>14$  drinks/week for men and  $>7$  drinks/week for women, where 1 drink = 5 ounces [150 mL] of wine or 12 ounces [360 mL] of beer or 1.5 ounces [45 mL] of hard liquor) or use of soft drugs (such as marijuana or any substances containing tetrahydrocannabinol (THC) or cannabidiol (CBD)) within 3 months prior to Screening, or hard drugs (such as cocaine) within 6 months prior to Screening.
36. Has a positive drug screen at Screening. **Note:** If benzodiazepines are detected on the drug screen, this is not exclusionary if they are prescribed a benzodiazepine for a therapeutic purpose (e.g. for insomnia) and confirmatory documentation is obtained from the prescribing physician.
37. Has known or suspected hypersensitivity to trial product(s) or related products.

38. Has a history of multiple significant and/or any severe allergies (e.g., food, drug, latex allergy) or has had an anaphylactic reaction or significant intolerance to prescription or nonprescription drugs or food.
39. Has previous participation in this trial. Participation is defined as signed informed consent.
40. Has participated in any clinical trial of an approved or non-approved investigational medicinal product within 90 days before screening.
41. Had major surgery or donated or lost 1 unit of blood (approximately 500 mL) within 4 weeks prior to the Screening Visit; has a screening hemoglobin <11.0 g/dL (males) or <10.0 g/dL (females), or has a known hemoglobinopathy (e.g. sickle cell anemia, hemolytic anemia).
42. Is a female who is pregnant, breast-feeding or intends to become pregnant during the planned course of the study. **Note:** Participants must have a negative serum pregnancy test ( $\beta$ -human chorionic gonadotropin ( $\beta$ -hCG)) performed by the central laboratory prior to enrollment in the study and prior to the randomization visit.
43. Is currently in violation of study requirements for prohibited and permissible concomitant medications or is anticipated to violate these requirements during study participation. These requirements are detailed in Section 10.1.
44. Has any disorder, unwillingness or inability, not covered by any of the other exclusion criteria, which in the investigator's opinion, might jeopardize the subject's safety or compliance with the protocol, or otherwise interfere with interpretation of efficacy and/or safety results.
45. Is unable or unwilling to follow to follow the study nutritional and physical activity counseling and to refrain from alternative lifestyle modification strategies throughout study participation. Refer to Section 11.1.
46. Is an employee or immediate family member (e.g., spouse, parent, child, sibling) of the Sponsor or study site.
47. Has any use of opiate medications within 14 days of screening or any anticipated/potential use of opiates during study participation.
48. Use of any other medications within 6 months of screening that, in the investigator's judgement, can significantly impact (increase or decrease) body weight, regardless of the purpose for their use.

**Note:** Rescreening/retesting is not permitted unless specified above.

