**Table 2: Study Schedule of Assessments (Continued)**

SOA													
	Screening Period	Treatment Phase by Week											ET or Post Study F/U
Visit Number	1	2 Rand.	3	4	5	6	7 g	8	9	10	11 g	12	13
Week e	~4 Weeks	Week 0	Week 1	Week 2	Week 3	Week 4	Week 5	Week 6	Week 8	Week 10	Week 12	EoT 13	Week 15
Study Day	-28	1	8	15	22	29	36	43	57	71	85	92	105
Visit Window (days)	0	0	±2	±2	±2	±2	±3	±3	±3	±3	±3	±3	±3
Heart Rate/Blood Pressure	X	X	X	X	X	X		X	X	X		X	X
Respiratory Rate/Temperature	X	X											X
Triplicate 12-lead ECG	X	X						X				X	
PHQ-9	X												
Laboratory and Safety Assessments													
General Safety Labs: Chemistry b, c	X	X				X			X			X	X
Fasting lipid Panel		X										X	
General Safety Labs: Hematology	X	X						X				X	X
Liver Function Test			X	X	X			X		X			
Urine Drug Screen	X												

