#### 5.11.4 Twelve-Lead Electrocardiogram

A triplicate 12-lead ECG will be collected at all specified timepoints as outlined in the SOA (Table 2).

The following parameters will be recorded on the eCRF from the subject's ECG trace: heart rate, QRS interval, PR interval, QT interval, and QT (corrected) (Fredericia's).

Trial sites will calculate the triplicate average QTcF at the screening visit to assess the QTcF exclusion criterion. No other calculation of ECG parameter averages is required for trial sites.

QTcF values and changes from baseline that reach the threshold of pre-defined limits of change as presented in Table 4 will be summarized using the number and percentage of subjects. Average of triplicates will be used to determine if subject meet pre-defined criteria.

ECGs as interpreted by the Investigator to be within normal limits, abnormal but not clinically significant, or abnormal and clinically significant, will be listed.

A by-subject listing for the ECG results will be provided.

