	2. Increase $\geq 1$ and value $>$ ULN
	3. Value > 5.4 and increased 15% above baseline
	4. Value $\geq 6.0$

<sup>b Differential red blood cell count will include mean corpuscular volume (MCV), mean corpuscular hemoglobin (MCH), mean corpuscular hemoglobin concentration (MCHC), red cell distribution width (RDW).

<sup>c MBA testing will include, in addition to above tests: estimated glomerular filtration rate (eGFR) measured by MDRD at screening

All Subjects	Increase ≥ 60 msec	
QTc Change from Baseline (	ms)	
Females	Value ≥ 470 msec	
Males	Value ≥ 450 msec	
QTc (ms)		
	2. Decrease≥ 1 and value < LLN	
Magnesium (mg/dL)	1. Increase≥ 1 and value > ULN	
	2. Decrease≥ 1 and value < LLN	
Calcium (mg/dL)	
 
Increase≥ 1 and value > ULN
 

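### SAP Table 4 counts QTcF at the limit that entry still allows, with no baseline condition or higher level, and its only change row (60 msec) will probably miss a moderate shift

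*Protocol*

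**What the plan says.** **Entry.** Protocol section 8.2, criterion 32, gives as the exclusion: "Has a corrected QT interval to Fridericia's formula (QTcF) $>450$ milliseconds (msec) for males and $>470$ msec for females at screening". Exactly 450 msec (men) or 470 msec (women) is therefore admitted. The criterion applies to the Screening ECG, where sites average the triplicate (Protocol 15.1.4). Baseline is the last pre-dose observation (SAP 5.1.2), normally the Day 1 ECG, and criterion 32 is not applied to it.

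**Analysis.** SAP 5.11.4 states that "QTcF values and changes from baseline that reach the threshold of pre-defined limits of change as presented in Table 4 will be summarized", and that "Average of triplicates will be used to determine if subject meet pre-defined criteria". The QTc rows of Table 4 (SAP Appendix 2) are "Value ≥ 450 msec" for males, "Value ≥ 470 msec" for females and "Increase ≥ 60 msec" for everyone. There are no other QTc rows.

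**ECG visits.** The schedule (Protocol Table 2) places the "Triplicate 12-lead ECG" at Screening, Day 1, Week 6 and end of treatment, which gives two post-baseline ECGs.

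**Other summaries.** Protocol 16.7.4 also promises ECG values and changes from baseline by treatment and timepoint. SAP 5.11.4 plans only the Table 4 counts and listings, while SAP section 8 declares no changes from the protocol. The vital-signs section just before it (SAP 5.11.3) does plan descriptive statistics by visit.

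**The concern.** The number that lets a person into the trial is also the number that marks an on-treatment outlier. Because entry excludes values strictly above the limit and Table 4 counts values at or above it, someone at the limit is counted with no change at all. The row also has no upper level, so a man at 451 msec and a man at 510 msec fall in the same cell.

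Other Table 4 parameters are handled differently. ALT and AST are admitted up to 2 times ULN, counted from 3 times ULN, and graded in four levels. Total bilirubin has an entry limit of 1.5 times ULN and is counted above 2 times. One potassium row ties the value to the participant's own baseline: "Value > 5.4 and increased 15% above baseline".

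The only QTc row based on change needs a rise of 60 msec on triplicate averages, so a moderate shift may leave no trace in it. Prior treatment lasted at most 28 days (Protocol 5.3), so this is the first 13-week ECG data set. With about 50 participants per arm, the reading of one or two counted cases depends on whether the values were new and how high they went.

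**Working it through.** The documents state no figure to reproduce here. They give the limits, 50 participants per arm (about 40 after the assumed 20% dropout) and two post-baseline ECGs. They give no QTcF mean, SD or expected drug effect, so those are assumptions and are shown as ranges.

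**1. Entering near the limit, no drug effect.** Take the screening value as the person's usual level, *d* msec below the limit, with an assumed SD of 8–12 msec for the difference between visits. The chance of being counted at one visit is 1 − Φ(*d*/SD):
- *d* = 0: 50%
- *d* = 5: 1 − Φ(5/8) = 27% to 1 − Φ(5/12) = 34%
- *d* = 20: 1 − Φ(20/8) = 1% to 1 − Φ(20/12) = 5%

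The problem is confined to people close to the limit.

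**2. The 60-msec row.** Per visit, *p* = 1 − Φ((60 − shift)/SD of change). With 50 per arm and two visits, P(row empty) = (1 − *p*)^100. For a 20-msec shift and SD 15, *p* = 1 − Φ(40/15) = 0.00383 and 0.99617^100 = 68%.

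| Mean shift | SD 10 | SD 15 | SD 20 |
|---|---|---|---|
| 10 msec | >99.9% | 96% | 54% |
| 20 msec | 99.7% | 68% | 10% |
| 30 msec | 87% | 10% | 0.1% |

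With 40 per arm and a 20-msec shift the figures are 99.8%, 74% and 16%. Treating the visits as independent understates the chance of an empty row. The largest shift that leaves the row empty at least half the time is 35, 23 or 11 msec for SD 10, 15 or 20.

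**3. The value row, by simulation.** Assumptions: mean QTcF 412 msec (men) and 425 msec (women), between-person SD 15–18, within-person SD 7–10 for a triplicate mean, 40% men, screened at criterion 32, one baseline and two on-treatment ECGs, 1,000,000 simulated participants per scenario. The implied SD of change is √2 × 7 = 9.9 to √2 × 10 = 14.1 msec.

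| | No effect | 10 msec | 20 msec |
|---|---|---|---|
| At or above 450/470 | 0.7%–2.3% | 3.8%–7.8% | 13%–19% |
| Rise of at least 60 | below 0.01% | at most 0.04% | at most about 0.45% |
| Rise of at least 30 | 0.2%–3% | 4%–13% | 25%–37% |

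Per 50 participants, the value row goes from 0.7%–2.3% × 50 = 0.35–1.15 with no effect to 13%–19% × 50 = 6.5–9.5 at 20 msec. Of the no-effect counts, 17%–28% had a baseline already at or above the limit, which is about 0.1 to 0.3 participants per 50.

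**4. A 30-msec level.** By the step 2 formula with 30 in place of 60, the expected count per visit in 50 participants (SD 10 to SD 15) is 0.07–1.1 with no effect, 1.1–4.6 at a 10-msec shift and 7.9–12.6 at a 20-msec shift. At SD 20 the no-effect rate would be 6.7% per visit.

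**The case against.** The strongest reply is that Table 4 already shows an effect. On the assumptions of step 3, a 20-msec shift puts roughly 6.5–9.5 of 50 participants in the value row, against about one or fewer on placebo. That stands. A reader might infer from the empty change row that the table as a whole would look reassuring; the value row contradicts this.

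A reader might also infer that people admitted near the limit could by themselves create or hide a difference between arms. The expected number already at or above the limit at baseline and counted again is only about 0.1–0.3 per 50. A baseline a few msec below the limit is not pre-existing, and a new-value rule would still count it.

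A third reply is that Protocol 16.7.4 plans mean changes by arm and visit. With 40 per arm and an SD of change of 10–20 msec, the standard error of an arm difference is SD × √(2/40) = 2.2–4.5 msec, so a 20-msec shift would be plain. This answers the concern under the protocol but not under the SAP, where 5.11.4 does not carry that summary over.

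Finally, participant listings will show each value, safety is descriptive with no formal tests, and nothing in the documents requires particular QTcF levels. All true. Listings do not, however, give an arm-level count of new values.

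**Conclusion.** The point holds as a table-design weakness of low severity. The documents alone establish that the Table 4 value limits equal the entry limits, that no baseline condition or higher level applies, that 60 msec is the only change level, and that SAP 5.11.4 omits the by-visit ECG summary in Protocol 16.7.4.

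The size rests on assumptions. The 60-msec row is more likely than not empty for a mean shift up to about 20 msec if the SD of change is about 15 msec or less. It would be too strong to say that the row stays empty whatever the effect: with an SD of 20 and a 20-msec shift, it is empty only about 10% of the time. Under the simulated means and SDs the value row responds clearly, and pre-existing values account for a minority of no-effect counts. The change therefore buys attribution and sensitivity to moderate rises; it does not rescue a blind table.

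**What to change.** In SAP Table 4 and section 5.11.4:

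1. Count 450/470 msec as new, meaning a post-baseline value at or above the limit with a baseline below it. Show participants at or above the limit at baseline on a separate line.
2. Add higher absolute levels, for example 480 and 500 msec and above. The documents prescribe none, so the sponsor should choose and justify them.
3. Add a row for an increase of at least 30 and less than 60 msec beside the 60-msec row.
4. Carry over the summary of ECG values and changes from baseline by arm and visit from Protocol 16.7.4, or declare its removal in SAP section 8.

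The cost is a few more table rows from ECGs already collected. Eligibility, treatment and visits are untouched, and SAP section 1 allows revision before database lock. The downside is chance cases in the 30-msec row in every arm: up to about 3% of participants under the simulated SDs, and more if the SD of change is nearer 20 msec. Read that row against placebo.
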